The study population for each outcome-specific SCCS analysis will be those subjects who experienced the event at least once during follow-up. Eligible person time for these subjects will be one month before the first recorded pertussis vaccine exposure until one month after the last pertussis vaccine exposure. Risk periods will be those specified for each outcome after each dose. Baseline periods will be days -31 to -8 before exposure and the interval from the last day of the risk window + 1 to day 31.

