### 7.2.7.2. Outcomes, Operationalization and Validation

#### OUTCOMES

The safety outcomes of interest are known reactions:

- Injection site reactions: erythema, edema, induration/ nodule/sterile abscess, pain/tenderness
- Fever
- Somnolence

- 
- Persistent crying, irritability
  - Generalized convulsions
  - HHE
  - Extensive limb swelling

A definition for somnolence is provided in Appendix 3. The Brighton Collaboration has case definitions available for injection site reaction [18], fever [19], persistent crying [20], generalized convulsions [21], HHE [22], and swelling (i.e. swelling at or near injection site as an increase in size or volume at the injection site that may extend to the entire limb according to severity) [23].

Events will be extracted from the electronic health care databases as diagnosis codes or text or by means of proxies. Mapping to ICD-9/10, READ and ICPC codes will be done semi-automatically using the ADVANCE code mapper. Algorithms for identification will be created with the databases and benchmarked against external sources and within consortium as described in section 7.1.

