### **VALIDATION**

Verification of the extracted codes and proxies for extraction of events will be done as part of the quality assessment and harmonization process (fingerprinting) prior to the start of the POC feasibility study. The verification will be done by comparing age-specific incidence rates between databases and comparison against external sources such as literature or other publicly available data. If possible, positive predictive values and sensitivity from prior studies will be retrieved. No chart validation at the patient level is foreseen for this POC feasibility study.

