### 7.2.8.3. Statistical Methods

#### COHORT STUDY

The incidence rate of each event will be calculated using a dynamic cohort approach. For each person in the cohort, follow-up time will be classified by calendar year, sex, age in year of birth and months and the different risk window (see exposure section). This persontime will be the denominator for the incidence rate calculations. Incidence rates will be calculated stratified by:

1. type of vaccine: wP/aP
2. database, country
2. dose of wP/aP (actually received dose)
3. risk window
4. age in months and year of birth
5. calendar year

[figure not shown]
Cases will be counted in the numerator for the rate calculation if the date of onset/occurrence of an event falls into the specific window of that vaccine, and will be further stratified to count in the correct age/sex and calendar year category at the date of onset.

A Poisson distribution will be used to calculate 95% CIs.

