  - The current methodology will not account for differences in vaccination schedules: different countries use different vaccines and schedules that may have changed over time. ATC codes will be used to identify which types of vaccines were used; this will allow stratification on vaccine types. Further, risks on schedule level will not be evaluated but will be evaluated on a dose level as each case is followed after each dose given.
  - Misclassification or missing information on vaccinations and events is a common limitation of observational studies conducted in electronic healthcare databases. Missingness and misclassification will be carefully followed and attempts will be made to implement data cleaning procedures (e.g. probability of wP or aP vaccine given the time of administration, dose according to timing in vaccination schedule, etc). Records with missing dates (i.e. birthdates, data of vaccination, date of event occurring) will be excluded. ATC code is a mandatory data field. A missing dose information will be derived (i.e., dose will be per recommendation, as determined by the database custodian based on knowledge of the local immunization schedule and as documented in an analytic variable generated for the purpose of the study).
  - aP and wP vaccine administration could have been overlapping. The period of potential overlap in a database will be excluded if aP or wP vaccine type information is missing (i.e. database entry is only referring to 'pertussis vaccine' and aP or wP is not specified).
  - The smallest possible time unit in electronic healthcare databases is 'days'. This could potentially make it difficult to judge whether vaccination happened before the event or vice versa when recorded on the same day. In this study, it is assumed a priori that vaccination occurs before the event whenever they are recorded on the same day, so the vaccination day is classified as risk period and starting at Day 0.

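### The SCCS post-dose baseline starts the day after a 24–72 hour risk window and makes no allowance for delay between onset and the recorded date, so late-dated reactions would bias the wP rate ratio downward

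*Protocol*

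**What the plan says.** Section 7.2.5 defines the SCCS baseline as two periods: "days -31 to -8 before exposure" and "the interval from the last day of the risk window + 1 to day 31". Days -7 to -1 before a dose are therefore in neither period. After the risk window there is no such buffer.

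The risk windows are in section 7.2.7.1:
- persistent crying and irritability: 0–24 hours
- somnolence and HHE: 0–48 hours
- fever and generalized convulsions: 0–72 hours
- injection site reactions and extensive limb swelling: 0–7 days

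On event dates, the cohort part of section 7.2.8.3 counts a case "if the date of onset/occurrence of an event falls into the specific window of that vaccine". Section 7.2.7.2 describes where events come from: "Events will be extracted from the electronic health care databases as diagnosis codes or text or by means of proxies". It adds: "No chart validation at the patient level is foreseen for this POC feasibility study". Section 7.2.9 notes that the databases work in whole days and states that "it is assumed a priori that vaccination occurs before the event whenever they are recorded on the same day".

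The abstract and section 7.2.1 then apply the wP ratio from the SCCS to databases that hold no wP data. The abstract says that it is multiplied by the baseline rate.

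**The concern.** The 24–72 hour windows describe when a reaction begins. An electronic record shows when it was seen or coded, unless the source also holds an onset date. Take a child vaccinated on Friday who cries persistently on Saturday (day 1) and is seen and coded on Monday (day 3). By recording date, this reaction falls outside the 0–24 hour window and, under section 7.2.5, counts as a baseline event.

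Such an event acts twice: it is removed from the numerator of the ratio and added to the denominator. Both effects lower the ratio, and a larger sample does not reduce them. The limitations section covers same-day ordering and misclassification in general, but not delay between onset and recording.

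At stake are the wP ratios and the wP rates built from them that feed the benefit-risk model. Under an equal late share, attenuation grows with the true ratio, so it would tend to narrow a wP–aP contrast.

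**Working it through.** **No figure to reproduce.** The protocol states no ratio, delay or late share for this point.

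**Inputs from the protocol.** Counting the hour-based windows in whole days from day 0, the risk days are w = 2 (0–24 h), 3 (0–48 h) and 4 (0–72 h). Baseline days for an isolated dose are B = 24 (days -31 to -8) + (31 − last risk day) = 54, 53 and 52.

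**Inputs assumed.** R is the true ratio and f is the share of excess (vaccine-caused) events dated after the window but by day 31. Neither is in the documents. R = 5 and 10 with f = 10% and 20% are used as a range. As a rough guide to f, suppose doses fall evenly on Monday–Friday, onset is even over the window, and every weekend onset is recorded on Monday. The late shares are then 1/10, 3/15 and 3/20 for the three short windows, and 0/40 for 0–7 days. The overshoot past the window is at most two days.

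**Formulas.**
- Baseline inflation: 1 + f(R−1)w/B
- Ratio as planned: [1 + (1−f)(R−1)] / [1 + f(R−1)w/B]
- Ratio if a gap catches all late records: 1 + (1−f)(R−1)

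**Results** (baseline inflation, then ratio as planned):

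| Window | R=5, f=10% | R=5, f=20% | R=10, f=10% | R=10, f=20% |
|---|---|---|---|---|
| 0–24 h | 1.5%, 4.53 | 3.0%, 4.08 | 3.3%, 8.81 | 6.7%, 7.69 |
| 0–48 h | 2.3%, 4.50 | 4.5%, 4.02 | 5.1%, 8.66 | 10.2%, 7.44 |
| 0–72 h | 3.1%, 4.46 | 6.2%, 3.96 | 6.9%, 8.51 | 13.8%, 7.20 |
| Any, with gap | 4.60 | 4.20 | 9.10 | 8.20 |

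Example: R = 10, f = 0.2, 0–72 h. Inflation is 1 + 0.2 × 9 × 4/52 = 1.138 and the ratio is 8.2/1.138 = 7.20. A simulation of the 0–72 h case with R = 6 and f = 0.2 gave 4.64 as planned and 5.00 with the late days excluded. The formulas give the same.

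**Split of the bias.** In the example, loss from the risk window takes 10 to 8.2, and baseline contamination takes 8.2 to 7.20. On the log scale the baseline part is ln(1.138)/ln(10/7.20), about 39%. For R = 2 to 6 and f of 10–40%, it is about 6–30% over the short windows. At R = 17 it is 31–54%.

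**Closely spaced doses.** Assume three doses on days 0, 30 and 60, a 0–72 h window, and every pre-dose gap kept. Distinct baseline days are 24 (-31 to -8) + 19 (4 to 22) + 19 (34 to 52) + 28 (64 to 91) = 90. With the same R at each dose, inflation at R = 10 and f = 20% is 3 × 0.2 × 9 × 4/90 = 24%, against 14% for an isolated dose.

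**The case against.** The strongest reply is that the premise is inferred. No sentence says that events carry a recording date. The cohort section names onset or occurrence, and section 7.2.9 lists the date on which the event occurred among the dates a record must hold. The same-day sentence there concerns only the order of vaccination and event. This stands. What remains is that the protocol asks for onset while describing no source for it and no allowance for delay.

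Other parts of the reply also hold:
- Deferral of every weekend event to Monday is a device, not a documented fact. Most listed databases hold inpatient diagnoses, and deferral is least plausible for convulsions and HHE.
- A gap alone leaves most of the bias at moderate ratios. Loss from the risk window also affects the cohort rates, which use the same windows.
- The pre-dose gap is no precedent. Section 7.2.8.3 ties the pre-vaccine period to the healthy-vaccinee effect.
- Section 7.2.9 warns that the estimates may not be the best or true ones. That does not justify an avoidable one-directional bias in a study that tests the method.

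Two stronger readings are tempting, and the documents do not support them. One is to apply the formula to the 0–7 day outcomes, where equal f gives much larger contamination; the weekend calculation gives no late records there. The other is that the extrapolated wP rate must be too low in every database without wP data. That would need a known delay in each database supplying a ratio. The receiving database's own cohort baseline also begins straight after the window, so late aP reactions could raise it and offset part of the loss.

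An unseen SAP does not settle the matter, because section 7.2.5 itself fixes the baseline days.

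**Conclusion.** The point holds conditionally. To the extent that events are dated by recording, the planned SCCS periods bias the wP ratio, and the rates extrapolated from it, downward. The direction follows from the definitions; the size is not known from the documents.

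For the five short-window outcome lines, with isolated doses and 10–20% recorded late, baseline contamination is about 1.5–6% at a true ratio of 5 and 3–14% at a ratio of 10. It is larger on schedules with closely spaced doses. Loss from the risk window is the larger part of the bias at moderate ratios. These figures rest on assumed ratios and late shares and on counting the windows in whole days. The changes are inexpensive and worth making, but the documents do not show the plan's estimates to be seriously wrong.

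**What to change.** 1. In section 7.2.5, for the 24–72 hour outcomes, make a short post-window period (for example 3–7 days) a separate level that is neither risk nor baseline. Report its events and its rate ratio. A raised ratio there would be direct evidence of delay.
2. Add a sensitivity analysis that extends each short risk window by about 3 days, with the baseline starting after the extension. Extra background days dilute the ratio, so compare (ratio − 1) × window days. For example, with R = 5, f = 20%, 0–72 h and all late records within 3 days, the extended ratio is 1 + 16/7 = 3.29. The excess is 2.29 × 7 = 16, equal to the true (5 − 1) × 4. With a gap alone it is 3.2 × 4 = 12.8.
3. In section 7.2.8.3, state that the event date is the onset date where the source holds one, and otherwise the recording date.

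Cost: a few sentences, one more period level in the scripts, and some precision. A 7-day gap removes about 7 of 52–54 baseline days for an isolated dose. For three doses 30 days apart with a 0–72 h window, it removes about 21 of 90 (23%). A 3-day gap would remove 3 of 52–54 and 9 of 90.

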#### **7.2.6. Study Period**

The study period is from 01 January 1990 to 31 December 2015, and also be dependent on availability of data from specific databases.

---

## 7.2.7. Variables

All study variables will be obtained from the participating electronic health care databases. These will be transformed their local datasets into a pre-defined ADVANCE common data model (CDM) to allow for the running of common scripts across all the databases.

### 7.2.7.1. Exposure of Interest, Operationalization and Validation

#### EXPOSURE OF INTEREST

The exposure of interest in this study will be all types of pertussis-containing vaccines that were available during the study period and used in the participating study population in the participating countries.

#### OPERATIONALIZATION

Vaccinations will be obtained from the databases by using names of vaccines and database specific codes. Vaccines will be categorized as wP, aP or unknown. There will be no further stratification in brand or product name (see Appendix 4 for categorization).

#### EXPOSURE WINDOWS

Person time of follow up in the cohort will be categorized as risk and baseline periods. Persons will be followed up over the whole period independent of occurrence of an event or vaccination. Person time will not be stopped at the occurrence of an event or vaccination. The vaccination day and outcome-specific risk-windows after vaccination will be classified as risk periods, and the period between the end of the risk-window after vaccination until the next pertussis-containing vaccination or end of follow-up as the baseline period. To keep track of dose, these periods will also be labelled by the number of previous pertussis-containing vaccinations.

---

Outcome	Risk Window After Vaccination
Injection site reactions	0-7 days
Fever	0-72 hours
Somnolence	0-48 hours
Persistent crying, irritability	0-24 hours
Generalized convulsions	0-72 hours
HHE	0-48 hours
Extensive limb swelling	0-7 days

---

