### **PERTUSSIS VACCINATION SCHEDULES IN EUROPE**

Between 2004 and 2015 several countries switched from wP to aP vaccines for infants and children. All other countries in Europe switched to aP vaccines prior to 2006 (starting in the 1990s for some countries). As of March 2015, all countries except Poland use exclusively aP vaccines. In most cases, the switch to aP vaccines was conducted over a narrow age-cohort, while only in very few cases, such as Poland, the switch occurred, or is occurring progressively over years. Different types of vaccines are being used. As part of the coverage pillar the way participating countries switched should be described.

Since the start of the introduction of pertussis vaccine in the 1940s, many countries have tended to adapt and customize the schedules of their vaccination programs, adding and removing doses, changing ages of primary and booster schedules, with or without catch-up campaigns, and transitioning from wP to aP vaccines for all doses, for one or more booster doses only, or not yet at all. As a result, pertussis vaccine schedules vary largely across Europe.

For detailed information on the schedules currently used in Europe, see Figure 2 and for more details see European Centre for Disease Prevention and Control (ECDC)-website (<http://vaccine-schedule.ecdc.europa.eu/Pages/Scheduler.aspx>).

---

 [http://www.nap.edu/openbook.php?record\\_id=13164&page=529](http://www.nap.edu/openbook.php?record_id=13164&page=529)

Schedule type	First year of life			Second year of life	Third year of life	Preschool booster	Adolescent booster	Country
	From 6 weeks to 6 months		Around first birthday					
'2p+1'	P1	P2	B1			B2	B3	F, IT, FI, NO, IS, SK
								SE, DK, RO, AT
'3p+1'	P1	P2	P3	B1		B2	B3	BE, BG, CZ, EE, DE, GR, HU, LI, LU,
				B1		B2		HR, CY, LV, LI, MT, NL, PL, PT, SI, ES
					B1			UK
						B1	B2	IE
Vaccine combination generally used in EU/EEA	
 
DTaP-IPV-HepB/Hib ('hexavalent')
 
DTaP-IPV/Hib ('pentavalent')
 
DTaP-IPV ('tetraivalent')
 
DTwP-IPV/Hib ('whole-cell pertussis combo')
 
Hep B (used in conjunction with pentavalent)
 
			
 
Hib-MenC combo
 
	
 
DTaP-IPV
 
Tdap
 
Tdap-IPV
 
Tdap
 
	
 
Td
 
Tdap
 
Tdap-IPV
 
		

P=primary dose; B=booster dose

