## VACCINE RISKS

### Safety Studies

In a study including 15,752 doses of diphtheria, tetanus, whole cell pertussis (DTwP) vaccine and 784 doses of diphtheria, tetanus (DT) vaccine performed in the Los Angeles area in 1978-1979, local redness, swelling and pain occurred in 37.4%, 40.7% and 50.9% of DTwP recipients compared with 7.6%, 7.6% and 9.9% of DT recipients, respectively. Frequencies increased in subsequent doses. Frequency of fever ( $\geq 38^\circ\text{C}$ ) was 46.5% and 9.3% after DTwP and DT, respectively. Furthermore, high-pitched unusual crying, convulsions and HHE following DTwP were reported in 0.1%, 0.06% and 0.06% recipients, respectively. Those events were not reported after DT, probably due to the low number of DT vaccinees [3].

---

A large study, performed in the USA, assessed common reactogenicity of 13 candidate aP vaccines compared to wP vaccine. For all adverse events following immunization (AEFIs), frequencies after aP vaccines were lower than after wP vaccines. For fever ( $\geq 37.8$  °C) frequency was 4.2% after the first dose of aP vaccine compared with 27.3% following wP vaccination. Temperature increased after subsequent doses. Incidence of local redness was 13.5% and 49.4%, local swelling was 8.7% and 39.7%, and local pain was 3.8% and 27.3% after aP and wP vaccination, respectively [10].

For rarer and more severe AEFIs, frequencies also differed. Persistent crying, very high fever ( $\geq 40.5$  °C), HHE and seizures were respectively 7, 7, 17 and 6 times more likely after vaccination with wP compared with aP [11].

In a large (n=28,796) questionnaire study carried out in the Netherlands between 2004 and 2007, frequencies of rarer, more severe AEFIs were higher after the Dutch wP vaccine (used until 2005) compared with the aP vaccine (introduced from January 1st 2005 onwards) [12]. In total, 1.5% of the infants reported prolonged crying  $\geq 3$  hours after first dose at two months after wP vaccination compared with 0.4% after aP. Frequencies of very high fever ( $\geq 40.5$  °C) after the fourth dose of wP and aP vaccines at 11 months were 0.8% and 0.2%, respectively, whereas frequencies for febrile convulsions after the fourth dose were 0.06% and 0.02%, and for HHE after the first dose were 0.12% and 0.03%, respectively.

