#### **7.2.5. Population Selection**

The study population will comprise all children registered in any of the participating databases during the study period and for whom an adequate start and end of follow-up and date of birth can be defined. Children will be followed from start of the study period, one month after date of birth (i.e. to allow for pre-vaccination time for the SCCS design and to avoid pre-term related or birth-induced increase in incidence rates), or date of valid data in the database (whichever is the latest) until the end of study period (31-12-2015, the school-entry pertussis booster, transferring out of the database, death, reaching age 6 years: whichever is the earliest). Persons with missing dates of birth or sex will not be included.

For the incidence rate part of the study, we will retain all subjects meeting age and calendar time inclusion criteria with person time greater than zero.

The vaccination day and outcome-specific risk-windows after vaccination will be classified as risk periods, and the period between the end of the risk-window after vaccination until the next pertussis-containing vaccination or end of follow-up as the baseline period. To keep track of dose these periods will also be labeled by the number of previous pertussis-containing vaccinations. For all eligible subjects, CohortStart will be equal to PopulationStart and CohortEnd equal to PopulationEnd.

Databases will be asked to provide dates during which both wP and aP pertussis vaccines were both being used in the population. Patient time during the period of the switch from wP to aP will be removed from the cohort and SCCS analyses to avoid misclassification of exposures.

In order to avoid confounding by infections or other vaccinations, the study population for the incidence rate cohort design will NOT be the same as for the SCCS design.

For the self-controlled case series, analysis sets containing cases of each of the outcomes under study will be defined. For each of these cases, exposure will be defined as: exposed to wP and exposed to aP.

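### aP doses given to children who started on wP are counted as plain aP doses; this mainly affects the toddler booster in the first months after the switch

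*Protocol*

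**What the plan says.** The exposure definition has two parts. Section 7.2.7.1 (Operationalization) classifies the single vaccination: "Vaccines will be categorized as wP, aP or unknown". The Exposure windows text in the same section, with near-identical wording in section 7.2.5, adds the dose label: "To keep track of dose, these periods will also be labelled by the number of previous pertussis-containing vaccinations". That label counts earlier doses of any type.

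Section 7.2.8.3 stratifies the cohort rates by vaccine type, database and country, received dose, risk window, "age in months and year of birth", and calendar year. Table 6 (section 7.3.1) then needs dose-specific incidences after wP or aP, by country and year of birth. For the self-controlled case series (SCCS), section 7.2.5 says: "For each of these cases, exposure will be defined as: exposed to wP and exposed to aP".

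Three other statements bear on the point:
- On the switch period, section 7.2.5 says (last word of the sentence left out): "Patient time during the period of the switch from wP to aP will be removed from the cohort and SCCS analyses to avoid misclassification of".
- Section 7.2.9 excludes the overlap period only where the vaccine type is missing.
- Section 7.2.9 also states that risks are evaluated by dose and not by schedule.

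None of these mentions children who began on one type and continued on the other.

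**The concern.** The research question is whether the profile held after the change from wP to aP, and section 5 (Figure 1 text) has the evidence accumulate from the switch onward. Children part-way through their series at the switch receive their remaining doses as aP. Their records enter the aP cells for dose 2, 3 or 4 and cannot be told apart from those of children vaccinated with aP throughout.

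These records are concentrated in the first months after the switch, when the simulated monitoring begins, and then die out. If a wP start changes the reaction to a later aP dose, the early aP booster rates would be biased as a description of the aP series. The fading of wP-started children could then look like a change over calendar time. The protocol treats vaccination history as relevant enough to count earlier doses, but it does not record their product, although product is what is being compared.

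**Working it through.** The protocol states no mixed-series share, so there is no figure to reproduce. The share can be derived from dates and ages that it does give.

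**Inputs**
- aP introduced on 1 January 2005, first dose at 2 months, fourth dose at 11 months: Dutch questionnaire study, section 5, Safety Studies.
- Doses 2 and 3 at 3 and 4 months: assumed for this example from the 2-3-4 schedule in section 5. The alternative there is 2-4-6.
- Febrile convulsions after dose 4, 0.06% (wP) and 0.02% (aP): same Dutch study.
- Assumptions: abrupt switch, steady births, all doses on time.

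**Rule.** Dose k, due at age a_k, given t months after the switch, belongs to a wP-started child if t < a_k − a_1. The lags are 3 − 2 = 1 month (dose 2), 4 − 2 = 2 months (dose 3) and 11 − 2 = 9 months (dose 4). On 2-4-6 they are 2 and 4 months for doses 2 and 3.

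**Mixed share of aP doses, nothing removed (2-3-4 plus 11 months)**

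| Months since switch | Dose 2 | Dose 3 | Dose 4 | Doses 2–4 together |
|---|---|---|---|---|
| 0–6 | 1/6 = 17% | 2/6 = 33% | 100% | 9/18 = 50% |
| 0–12 | 1/12 = 8% | 2/12 = 17% | 9/12 = 75% | 12/36 = 33% |
| 0–24 | 1/24 = 4% | 2/24 = 8% | 9/24 = 38% | 12/72 = 17% |

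For the first 9 months there is no all-aP dose-4 group at all.

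**Switch-period removal.** If the first r months are removed, the dose-4 share in the next 12 months is max(0, 9 − r)/12. That is 8/12 = 67% for r = 1, 6/12 = 50% for r = 3, 3/12 = 25% for r = 6, and 0% for r = 12. Removal works on calendar dates, so a wP-started child's aP dose after the removed period stays in.

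**Birth-year strata.** Dose 4 in 2005 goes to children born from February 2004 to January 2005. Those born from February to October 2004 (9 monthly cohorts) had their first dose before the switch. The 2004 birth year contributes 11 cohorts to aP dose 4, so 9/11 = 82% of that cell is mixed. In later birth years the share is 0%.

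**What this could do to a rate.** Let f be the mixed share and m the risk in mixed-series doses relative to all-aP doses. The observed aP rate is 0.02% × ((1 − f) + f × m). The documents give no value for m, so a range is shown, treating 0.02% as an all-aP rate, with f = 0.75:

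| m | aP dose-4 rate | wP/aP ratio |
|---|---|---|
| 0.5 | 0.0125% | 4.8 |
| 1 | 0.0200% | 3.0 |
| 1.5 | 0.0275% | 2.18 |
| 2 | 0.0350% | 1.71 |
| 3 | 0.0500% | 1.20 |

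At m = 1 nothing changes.

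**The case against.** The strongest reply is that dose-level analysis is a declared choice, that existing provisions contain the problem, and that no harm is shown. Much of this stands.

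- **Mechanism.** Section 5 reports of one study: "Temperature increased after subsequent doses". A reader might infer that prior product therefore matters. The statement shows an effect of dose number, which the plan already tracks. It does not show that wP priming alters the reaction to a later aP dose.
- **Extent.** A reader might infer that most later aP doses after the switch are mixed. That is true only of the first months or of the toddler booster. Over the first year, doses 2 to 4 together are 33% mixed on this schedule.
- **Existing protection.** Birth-year strata confine the problem to one identifiable row in the Dutch example, and a long enough removed period abolishes it. However, that row would still enter Table 6 labelled as aP. Section 5 says most switches covered a narrow age-cohort, so the removed period may be short.
- **Booster-only transitions.** Section 5 describes countries "transitioning from wP to aP vaccines for all doses, for one or more booster doses only, or not yet at all". One could infer wholly mixed aP boosters for some birth years. No participating database is shown to have had such a transition, a literal reading of section 7.2.5 might remove those years, and follow-up ends at the school-entry booster in any case.
- **SCCS.** The ratio carried to other databases is wP versus baseline. In a wP-to-aP switch, wP doses follow wP doses, so that ratio is not diluted.

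The dose-level limitation in section 7.2.9 concerns differing schedules and does not cover mixed series. Leaving the matter to an analysis plan is not a full answer either, because the protocol itself fixes the label without series history.

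**Conclusion.** The point holds in a limited form. The exposure label omits the type of earlier doses, so aP doses in wP-started children are counted as aP doses of that number. The effect is material for the toddler booster just after the switch: 100% of aP dose 4 for 9 months, 75% over the first year and 82% of the preceding birth year's aP dose-4 cell. These figures assume an abrupt switch, steady births, on-time doses and no removed period. For doses 2 and 3 it passes within 1 to 2 months on 2-3-4, or 2 to 4 months on 2-4-6.

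The documents do not support saying that the wP–aP comparison is confounded. They support saying that early aP booster rates and their calendar-time trend could be biased if wP priming matters, and that the planned label gives no means of checking. The study tests no hypothesis, but these rates feed the benefit-risk model. This is a worthwhile, low-cost improvement and not a fatal flaw.

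**What to change.** - In the cohort analysis, add a derived label from dose 2 on: earlier doses all wP, all aP, or mixed/unknown.
- Keep the overall aP dose-specific and calendar-time rates, and also show them split by this label. Add a sensitivity version of Table 6 restricted to homogeneous series.
- Reconcile the switch-period exclusion in section 7.2.5 with the narrower one in section 7.2.9, since the size of the problem depends on which applies.
- Name mixed series as a limitation in section 7.2.9.

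The cost is one variable built from vaccination dates and types that are extracted anyway. The downside is sparse all-aP dose-4 cells after the switch, empty for the first 9 months in the Dutch example. For that reason the homogeneous-series version should accompany the overall rates and not replace them.
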